### 3.2 UNL

For the first six subjects who consent for additional PK collections at Georgetown University, blood will be collected for pharmacokinetic study on Visit 1 (day 1 of week 1): pre-dose and at 1.5, 3.5, and 8.5 hours (+/- 5 minutes) after the first dose of Polyphenon E under fed conditions. Study subjects will self-collect their urine before dosing and at three intervals during the 24-h period after dosing (0–4, 4–8, and 8–24 h)..

All subjects will have a clinic visit at Screen 1, Screen 2, Visit 1 (week 1 day 1), Visit 2 (week 13 +/- 3 days), Visit 3 (week 25 +/- 3 days, end of treatment), Visit 4 (week 28 +/- 7 days, end of study visit), described in detail in Section 7.1. The laboratory tests at Screen 1 and Visits 1-4 include CBC, chemistry and liver function tests (CMP), and coagulation tests. Following the FDA mandate, weekly or bi-weekly (depending on assigned dose, clinical stability, and liver biochemical stability of the participant) liver function & coagulation tests will be carried out for safety monitoring.

An ultrasound, CT or MRI scan will also be performed after consent and prior to starting agent unless it has been done per standard of care within three months from the consenting date and showed no evidence of HCC. It will also be performed at the end of intervention (Visit 3  $\pm$  3 weeks) as part of standard of care. The imaging performed at the beginning and end of intervention must be the same method (i.e. if an ultrasound was used or performed during screening, then an ultrasound must be performed at the end of intervention). These evaluations will detect any HCC development during the treatment.

FibroScan will be performed after consent and prior to starting agent as part of standard of care unless the scan has been done within three months from the consenting date. It will also be performed at the end of intervention (Visit 3  $\pm$  3 weeks) as a research procedure. These evaluations will evaluate the change of liver stiffness after six months of Polyphenon E treatment.

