### 5.1 Dose Regimen and Dose Groups

The treatment to be used in this trial is outlined below in Table 3:

**Table 3:** Trial Treatment

| Drug         | Dose/
Potency | Dose
Frequency | Route of
Administration | Regimen/
Treatment
Period | Use          |
|--------------|------------------|-------------------|----------------------------|---------------------------------|--------------|
| Polyphenon E | 400 mg EGCG      | daily             | oral                       | Continuously
for 24 weeks    | Experimental |
|              | 400mg EGCG       | bid               |                            |                                 |              |
|              | 600mg EGCG       | bid               |                            |                                 |              |
|              | 800mg EGCG       | bid               |                            |                                 |              |
|              | 1000mg EGCG      | bid               |                            |                                 |              |

On an outpatient basis, Polyphenon E will be administered orally according the dose level of

EGCG assigned for each cohort on a continuous dosing schedule for 24 weeks.

The medication will be released on Visit 1 (week 1, day 1); and Visit 2 (week 13 +/- 3 days). A participant diary will be provided to participants and collected from them by the study coordinator approximately every 12 weeks during clinic visits for the 24 weeks of treatment. Thus participants will have their diary reviewed and a pill count performed at their Visit 2 (week 13 +/- 3 days) and at Visit 3 (end of intervention, 25 +/- 3 days).

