## 7. CLINICAL EVALUATIONS AND PROCEDURES

### 7.1 Schedule of Events

|   | Pre-Screen | Screen 1 a
(0-60 days prior to registration) | Screen 2 a
(0-60 days prior to registration) | Visit 1: Week1 Day 1 (0-14 days after registration) | Between Visits 1 and Visit 2 | Visit 2: Week 13 +/- 3 days) | Between Visits 2 and 3 | Visit 3: End of Treatment (week 25 +/- 3 days) | Visit 4: End of Study (week 28+/- 7 days) |
|---|------------|--|--|---|------------------------------|------------------------------|------------------------|--|---|
| Pre Screen Eligibility performed by investigator b                       | x          |  |  |   |                              |                              |                        |  |   |
| Informed consent  |            | x  |  |   |                              |                              |                        |  |   |
| Medical History   |            | x  |  |   |                              |                              |                        |  |   |
| Concomitant Medications Collection  |            | x  |  | x   |                              | x                            |                        | x  |   |
| Adverse Events Assessments  |            |  |  | x   |                              | x                            |                        | x  |   |
| Physical Examination c   |            | x  |  | x   |                              | x                            |                        | x  | x   |
| Vital Signs (temperature, pulse, respiratory rate, and blood pressure) c |            | x  |  | x   |                              | x                            |                        | x  | x   |
| Pregnancy test  |            | x  |  | x d                                      |                              |                              |                        |  |   |
| Ultrasound, CT or MRI Scan Abdomen e                                     |            |  | x  |   |                              |                              |                        | x  |   |
| FibroScan f  |            |  | x  |   |                              |                              |                        | x  |   |
| Venipuncture for clinical labs  |            | x  |  | x   |                              | x                            |                        | x  | x   |

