- h. In between Visits 1 and 2, and between Visits 2 and 3, liver function & coagulation tests including AST, ALT, alkaline phosphatase, total protein, albumin, direct bilirubin, indirect bilirubin, total bilirubin, magnesium, GGT, calcium, phosphorus, and INR will be performed according to the schedule below. These tests will be performed at the central lab, or, if the participant prefers, at a local clinic lab. Participants who experience hepatotoxicity according to Appendix D will be re-evaluated every 3-4 days until resolution.
  - a. For participants assigned to 400 mg EGCG QD or 400 mg EGCG BID: bi-weekly liver function & coagulation testing (every 14 +/- 3 days).
  - b. For participant assigned to  $\geq$ 600 mg EGCG BID: weekly liver function & coagulation testing (every 7 +/- 3 days) for the first 2 weeks on agent, or until the participant demonstrates stability of clinical condition and liver biochemical enzymes\* for at least 2 weeks, whichever is longer. Thereafter, the participant will receive bi-weekly liver function & coagulation testing (every 14 +/- 3 days).

\*Stability of clinical condition and liver biochemical enzymes is defined as meeting all of the following, as listed in Appendix D:

- a. No symptoms of clinical hepatitis (vomiting, nausea, right upper quadrant pain)
- b. No ALT or AST increases to  $\geq$ 5x upper limit of normal
- c. No ALT or AST increases to  $\geq$ 3x baseline levels
- d. No elevations in direct bilirubin  $>$  1.5 ULN
- e. No elevation of direct bilirubin  $>$  ULN, regardless of ALT or AST levels, with indicators of immunological reaction (i.e., rash or  $>$ 5% eosinophilia).

- i. For details on the Child-Pugh score, see [https://www.qxmd.com/calculate/calculator\\_43/child-pugh-score](https://www.qxmd.com/calculate/calculator_43/child-pugh-score).
- j. Only the subjects with  $\gamma$ -OHPdG-high in the base-line liver biopsy will be registered for treatment. The treatment is to start within 14 days from registration. The subjects with  $\gamma$ -OHPdG-low liver

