Participants will complete weekly or bi-weekly liver function & coagulation tests according to the chart below. These tests can be done with local lab or MD, for convenience; LabCorp or Quest are preferred, as the results will be reported directly to hospital electronic medical chart. If another lab is used, the report can be requested to be faxed to the investigator and/or study coordinator.

- Venipuncture for clinical labs
- Liver function tests, including ALT, AST, direct bilirubin, indirect bilirubin, and total bilirubin, alkaline phosphatase, total protein, albumin, GGT, calcium, phosphorous, and magnesium
- Coagulation test (INR)

| Assigned Dose  | Schedule of liver function & coagulation tests  |
|--|---|
| 400 mg EGCG QD or
400 mg EGCG BID   | Bi-weekly liver function & coagulation testing (every 14 +/- 3 days)  |
| $\geq$ 600 mg EGCG BID   | Weekly liver function & coagulation testing (every 7 +/- 3 days) for the first 2 weeks on agent, or until the participant demonstrates stability of clinical condition and liver biochemical enzymes* for at least 2 weeks, whichever is longer. Thereafter, the participant will receive bi-weekly liver function & coagulation testing (every 14 +/- 3 days). |
| * Stability of clinical condition and liver biochemical enzymes is defined as meeting all of the following, as listed in Appendix D: |   |

- a. No symptoms of clinical hepatitis (vomiting, nausea, right upper quadrant pain)
- b. No ALT or AST increases to  $\geq 5$ x upper limit of normal
- c. No ALT or AST increases to  $\geq 3$ x baseline levels
- d. No elevations in direct bilirubin  $> 1.5 \times$  ULN.
- e. No elevation of direct bilirubin  $>$  ULN, regardless of ALT or AST levels, with indicators of immunological reaction (i.e., rash or  $> 5\%$  eosinophilia).

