### Study Visit 2 (Week 13 +/-3 days)

After taking the study medication for 12 weeks +/-3 days, participants will return to the clinic.

- Record Concomitant Medications
- Physical Exam & Vital Signs
- Adverse Events Assessments.
- Venipuncture for clinical labs
- Clinical Labs – including CBC with differential and platelets, comprehensive metabolic panel including BUN, creatinine, sodium, potassium, chloride, calcium, bicarbonate, glucose, liver function tests including AST, ALT alkaline phosphatase, total protein, albumin, direct bilirubin, indirect bilirubin, total bilirubin, magnesium, GGT, and phosphorous, coagulation test (INR), AFP and AFP-L3.
- Research Urine collection (compliance)
- Research Blood collection (for  $\gamma$ -OHPdG level)
- Dispensation of study drug
- Participant diary review and unused pill count
- Give participant blank participant diary

### Between Visits 2 and 3

Participants will complete weekly or bi-weekly liver function & coagulation tests according to the chart below. These tests can be done with local lab or MD, for convenience; LabCorp or Quest are preferred, as the results will be reported directly to hospital electronic medical chart. If another lab is used, the report can be requested to be faxed to the investigator and/or study coordinator.

- Venipuncture for clinical labs
- Liver function tests, including ALT, AST, direct bilirubin, indirect bilirubin, total bilirubin, alkaline phosphatase, total protein, albumin, GGT, calcium, phosphorous, and magnesium
- Coagulation test (INR)

| Assigned Dose                        | Schedule of liver function & coagulation tests   |
|--------------------------------------|--|
| 400 mg EGCG QD or
400 mg EGCG BID | Bi-weekly liver function & coagulation testing (every 14 +/- 3 days)   |
| $\geq 600$ mg EGCG BID               | 
If the participant has previously demonstrated stability of clinical condition and liver biochemical enzymes* for at least 2 weeks, the participant will receive bi-weekly liver function & coagulation testing (every 14 +/- 3 days).
 
If the participant has not already demonstrated stability of clinical condition and liver biochemical enzymes* for at least 2 weeks, the participant will receive weekly liver function & coagulation testing
 |

|   |   |
|---|---|

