## **8. CRITERIA FOR EVALUATION AND ENDPOINT DEFINITION**

### **8.1 Primary Endpoint**

8.1.1 To establish maximum tolerated dose (MTD) and to collect safety data of Polyphenon E/EGCG treatment in participants with cirrhosis

The safety data of Polyphenon E treatment in participants with liver cirrhosis will be collected at the monthly visit for the first 3 cycles, then at the end of treatment visit for 4th to 6th cycle of treatment). Safety data on hepatotoxicity will be obtained by weekly or bi-weekly (depending on assigned dose, clinical stability, and liver biochemical stability of the participant) liver function tests. Participants who experience hepatotoxicity according to Appendix D will be re-evaluated every 3-4 days until resolution.

Safety and adverse event data will be summarized using descriptive (frequency, %) statistics by dose cohort. The primary endpoint of MTD cannot be established because the study was closed early, and, based on the observed safety profile with a single DTC occurring in dose cohort 4 (1/4 patients), future studies can consider dose level 3 as the starting dose.

8.1.2 To determine the effects of Polyphenon E/EGCG treatment on the suppression of  $\gamma$ -hydroxy-1,N(2)-propanodeoxyguanosine ( $\gamma$ -OHPdG) levels in cirrhotic liver.

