### **15. FINANCING, EXPENSES, AND/OR INSURANCE**

Study subjects will be provided with a compensation as follows:

- \$200 for each liver biopsy (at Screen 2 and at Visit 3)
- \$75 for each clinic visit, for transportation, parking, childcare, etc. (Screen 1, Screen 2, Visit 1, Visit 2, Visit 3, and Visit 4).
- \$25 for each weekly/bi-weekly blood draw between visits (max of 14). Participants will be provided \$25 for the blood draw even if it is performed at an outside clinic.

The maximum total provided to each participant, depending on the requirements of their participation, is \$1,200.

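### Section 8.1.1 relies on monthly safety visits that the schedule does not contain, so non-laboratory DTC events have no dated check between Day 1 and week 13

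*Combined protocol and SAP*

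**What the plan says.** **Safety collection.** Section 8.1.1 states that safety data "will be collected at the monthly visit for the first 3 cycles, then at the end of treatment visit".

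**Visits.** Section 3.2 lists them: "All subjects will have a clinic visit at Screen 1, Screen 2, Visit 1 (week 1 day 1), Visit 2" at week 13, Visit 3 at week 25 and Visit 4 at week 28. In the section 7.1 table, the row "Adverse Events Assessments" is marked at Visits 1, 2 and 3 and is blank between Visits 1 and 2. Section 7.3 describes Visit 2 as follows: "After taking the study medication for 12 weeks +/-3 days, participants will return to the clinic". Section 15 pays "for each clinic visit, for transportation, parking, childcare, etc. (Screen 1, Screen 2, Visit 1, Visit 2, Visit 3, and Visit 4".

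**Between Visits 1 and 2.** Liver tests and INR are scheduled every two weeks at the two 400 mg levels. From 600 mg BID the plan asks for "weekly liver function & coagulation testing (every 7 +/- 3 days) for the first 2 weeks on agent", or for longer if the participant is not yet stable. Section 7.3 says of the draws: "These tests can be done with local lab or MD, for convenience". Under section 5.1 the diary is "collected from them by the study coordinator approximately every 12 weeks during clinic visits".

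**What depends on the first four weeks.** Section 3.1 holds the next cohort until each cohort has been followed for four weeks for DTC. Section 13.1 defines the MTD by DTC in the same period. DTC has three limbs: (a) related grade 3 or higher toxicity, (b) discontinuation required by Appendix D, and (c) hepatic decompensation.

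**The concern.** MTD and safety are a primary endpoint, and cohorts hold three or four people, so one event found or missed changes a cohort's count. DTC is wider than liver tests and INR can show. Section 6.2 reports related grade 3 abdominal pain, dyspepsia, diarrhea, fatigue and rectal hemorrhage with this agent, none of which need alter those tests. If sites follow the section 7.1 table, a cohort can be cleared without anyone having been scheduled to ask about such events.

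Appendix D adds a smaller difficulty. Limb (b) turns on discontinuation, and the appendix is not uniform about when treatment stops and when it may restart.

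**Working it through.** **1. The plan's own payment total.** Inputs from section 15: $200 per biopsy (2), $75 per clinic visit (6 named), $25 per interim draw (maximum 14).

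2 x 200 + 6 x 75 + 14 x 25 = 400 + 450 + 350 = 1,200, which equals the stated maximum.

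Two further clinic visits, at weeks 5 and 9 for example, would give 1,200 + 2 x 75 = 1,350. The payment list therefore agrees with the section 7.1 table and not with section 8.1.1.

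**2. Dates of AE assessment.** Take first dose as day 1 and day = 7 x (week - 1) + 1. The DTC window is days 1-28.

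- Visit 1: day 1.
- Visit 2: 7 x 12 + 1 = 85, +/- 3, so day 82-88.
- Visit 3: 7 x 24 + 1 = 169, +/- 3, so day 166-172.

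Scheduled AE assessments on days 2-28: none. Gap from window close to Visit 2: 82 - 28 = 54 to 88 - 28 = 60 days.

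With four-week cycles, as in the pharmacokinetic text of section 8.2.1, the first monthly visit of section 8.1.1 would fall near day 29, where the window closes.

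**3. Laboratory draws around the window.**

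| Dose | Nominal draws (range) | Count, nominal | Count if last draw falls after day 28 |
|---|---|---|---|
| 400 mg QD or BID | 15 (12-18), 29 (26-32) | 2 | 1 |
| 600 mg BID and above, stable | 8 (5-11), 15 (12-18), 29 (26-32) | 3 | 2 |

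The nominal count includes the four-week draw. An unstable participant from 600 mg BID also has a draw at day 22.

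**4. Each part of DTC against what is dated inside the window after Day 1.**

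| DTC component | Dated check |
|---|---|
| Laboratory criteria of Appendix D | Yes: liver tests and INR |
| Hepatitis symptoms (vomiting, nausea, right upper quadrant pain) | From 600 mg BID, implied by the stability rule but undated; at the 400 mg levels, only once a test is abnormal |
| Related non-hepatic grade 3 or higher toxicity | None |
| Clinical decompensation without a laboratory trigger | None |

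**5. Appendix D, texts side by side.**

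- The table and item 1: for a symptomatic ALT or AST rise to at least 3 times baseline, interrupt; restart needs a firm competing cause and a return to baseline.
- Close observation, item 5: a symptomatic patient's drug is to be stopped at once, using the verb discontinue.
- Follow-up procedures: re-initiation is allowed once abnormalities stabilize.

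The first and third texts give different restart conditions. The second does not say whether the stop counts under limb (b).

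**6. Escalation wording.** Section 2.5.2 opens the next level on Appendix D discontinuations alone, and section 13.9 speaks of liver toxicities. Sections 3.1 and 13.1 use all three limbs.

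**7. Why a missed event matters (assumed rates, not from the plan).** For a standard 3+3 with observed DTC probability q, P(escalate) = (1 - q)^3 + 3q(1 - q)^2 x (1 - q)^3. At a true rate of 33%, this is 43% if every DTC is seen (q = 0.33), 61% if three quarters are seen, and 78% if half are seen (q = 0.165).

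**8. Table 6 with exact (Clopper-Pearson) 95% intervals.** Cohorts 1-3: 0/3, 0-71%. Cohort 4: 1/4, 0.6-81%. These widths reflect cohort size and would be the same under any visit schedule.

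**The case against.** The strongest reply is that the window is monitored. Section 3.1 itself requires four weeks of observation for all DTC limbs. Liver tests and INR are dated. From 600 mg BID, which covers cohorts 3 and 4 and so the only DTC, the move to two-weekly testing requires that hepatitis symptoms be absent. All of this stands, and it rules out two stronger readings that a reader might draw: that no AE assessment lies in the window at all (Visit 1 on day 1 has one), and that only laboratory data bear on it.

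The plan has other safeguards: extra AE assessment when clinically indicated (7.6), reassessment within days of a toxicity (5.6), the study-hold rule (8.5), telephone reporting of serious events (11.2.2) and monthly medical-monitor review (12.4). Each acts on an event that has already surfaced. The section 3.1 obligation has no visit or contact attached to it.

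On Appendix D, a reader might infer a flat contradiction between interrupting and discontinuing. The text does not support that. The close-observation list opens with interruption, and a final stop is elsewhere expressly called permanent. Item 5 is best read as an immediate stop. The difference in restart conditions remains.

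Finally, enrolment ended at 13 and the plan declares the MTD not established, so no escalation decision is pending. Section 13.5 already calls for 95% intervals, and section 11.1.2 requires onset dates. This narrows the remaining work but does not remove it.

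**Conclusion.** The point holds in limited form and should be fixed. Section 8.1.1 conflicts with the schedule and the payment list. Between Day 1 and day 82-88 no AE assessment is scheduled, so DTC components without a laboratory trigger depend on spontaneous reporting or on assessment when clinically indicated. Appendix D needs one restart rule and a statement of how an immediate stop counts.

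A reader might infer that Table 6 missed events. The documents do not show that, and the counts may be complete. Table 6 does not state its DTC window. Four weeks is the natural reading, but section 8.3 applies the same criteria as an off-agent rule without a time limit. The label matters because sections 8.1.1 and 13.4 use the single DTC in cohort 4 to suggest dose level 3 as a starting dose for future studies.

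The conclusion assumes first dose on study day 1. The consent pages, the flow schema, the diary form and the master monitoring plan were not available to this review, so a reporting instruction there cannot be ruled out.

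**What to change.** **Further enrolment or a successor protocol.** Do not simply delete the monthly visits from section 8.1.1, since that is the only text placing a regular safety check in the early cycles. Reconcile it with section 7.1 by adding a documented AE/DTC contact at the existing draws in the first four weeks, by phone if the draw is off-site. Complete the last contact before the next cohort opens, timed so that it covers the window through day 28.

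**Appendix D and wording.** State one restart rule; the table's rule (firm competing cause plus return to baseline) is the more specific and the safer. Say whether an immediate stop under close observation counts under DTC limb (b). Align sections 2.5.2 and 13.9 with the DTC in sections 3.1 and 13.1.

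**The 13 treated participants.** Label Table 6's DTC window. From recorded onset dates, report DTC by cohort for the first 4 weeks and for 24 weeks, with exact 95% intervals. Note that non-laboratory events between Day 1 and Visit 2 were not actively solicited on a schedule.

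**Cost.** Two or three brief contacts per future participant, text edits, one table label, and a check of onset dates for 13 people.

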## 8.2 Secondary Endpoints

8.2.1 To collect Polyphenon E/EGCG pharmacokinetic data in participants with cirrhosis.

In previous preclinical studies, the pharmacokinetics of the conjugated metabolites of EGC and EC were not affected by repeat green tea polyphenol daily treatment for 4 weeks. A limited sampling strategy was developed to predict EGCG pharmacokinetics after green tea administration (38). The median sampling times were 0.7, 1.4, and 7.0 hours (fasting conditions) and 1.4, 3.6, and 8.7 hours (fed conditions). The sampling schemes were accurate and precise in predicting EGCG

oral clearance and exposure (area under the curve [AUC]) under both fasting and fed conditions. In this current study, blood and urine samples will be collected in six subjects on day 1 of a 4 week cycle, prior to the first dose of Polyphenon E, and then at 1.5, 3.5, and 8.5 hours (+/- 5 minutes) after the first dose of Polyphenon E, taken while fed. Clearance of Polyphenon E will be compared among cirrhotic liver participants in this study and results from this population will be compared with non-cirrhotic historical control participants (38).

8.2.2 LC-MS assay will be used to determine gamma-OHPdG changes from baseline to post-treatment. This will generate a continuous variable for values of gamma-OHPdG. Descriptive statistics (mean, range) will be used to summarize this continuous outcome by dose level. A nonparametric trend test will be used to examine whether there is a trend for greater reduction in gamma-OHPdG as the dose level increases.

8.2.3 To estimate the fraction of participants with liver cirrhosis that have high levels of  $\gamma$ -OHPdG.

The fraction of participants with liver cirrhosis that have high levels of  $\gamma$ -OHPdG is calculated based on the number of subjects enrolled over the number of subjects screened based on the levels of  $\gamma$ -OHPdG in their first liver biopsy.

8.2.4 Exploratory Endpoint: To assess the effects of Polyphenon E on the grade of cirrhosis as measured by FibroScan and FIB-4 score.

Whether Polyphenon E treatment affects the level of cirrhosis will be evaluated by comparing the reading of FibroScan at baseline and 6 months of EGCG treatment in the subjects participating the intervention study.

8.2.5 Exploratory Endpoint: To develop an LC-MS and/or ELISA-based method for detecting  $\gamma$ -OHPdG.

The research urine samples at Screen 2 and research blood samples collected at Visit 1, Visit 2, and Visit 3 will be used to develop a non-invasive LC-MS and/or ELISA-based method to quantify  $\gamma$ -OHPdG in urine and blood samples of collected from trial participants.

